## 6.4. WINDOWING CONVENTIONS

Windows for PAC1, PAC2 and PAC3 are to be applied based on scheduled visit dates as defined in Section 3.1 General Description.

For inclusion in the PP population a window is to be defined for the PAC3 period only. The window start date is defined as the planned Visit 4E date  $\pm$  10 days, relative to the Visit 3A date (Baseline), that is, 50 weeks after the Baseline date  $\pm$  10 days. Similarly, the window end date is defined as the planned Visit 4F date  $\pm$  10 days, that is, 52 weeks after the Baseline date  $\pm$  10 days.

Any subjects for whom being out of window doesn't affect whether or not their symptoms might have been confounded with seasonal allergies are also to be included. For this latter category, a review is to be done manually by Circassia.

Review of the PAC3 windows and decisions regarding inclusion/exclusion form the PP population is to be documented in the BDR meeting minutes.

## 6.5. STATISTICAL TESTS

The default significance level is to be 5%; confidence intervals are to be 95% and all tests are to be two-sided, unless otherwise specified in the description of the analyses.

## 6.6. COMMON CALCULATIONS

For quantitative measurements:

- Change from Baseline is to be calculated as
  - Test Value at Visit X – Baseline Value

---

Document: TH005 SAP Version 2.docx  
Author: [name]

Version Number: 2.0  
Version Date: 24MAR2017

Template No: CS\_TP\_BS016 – Revision 3  
Effective Date: 01May2012

Reference: CS\_WI\_BS005

Copyright © 2012 Quintiles Transnational Corp. All rights reserved.  
The contents of this document are confidential and proprietary to Quintiles Transnational Corp. Unauthorized use, disclosure or reproduction is strictly prohibited.

---

- Percentage change from Baseline is to be calculated as
  - $[(\text{Test Value at Visit X} - \text{Baseline Value}) / \text{Baseline Value}] \times 100$
- Descriptive statistics are to include n, mean, standard deviation (SD), median, minimum and maximum

For qualitative measurements (e.g. Gender):

- Summaries are to include frequency (n) and percentage (%) of subjects. Percentages are to be calculated as either
  - The number of subjects within a category relative to the total number of subjects in the relevant analysis population with data available. In this case a missing category is to be added to indicate the number of subjects with no data and the missing counts are not to be included in the denominator for the percentage calculation, or
  - The number of subjects in a category relative to the total number of subjects in the relevant analysis population

The applicable method of percentage calculation is indicated in each relevant analysis section.

## 6.7. SOFTWARE VERSION

All analyses are to be conducted using SAS Version 9.4 or higher.

---

Document: TH005 SAP Version 2.docx  
Author: [name]

Version Number: 2.0  
Version Date: 24MAR2017

Template No: CS\_TP\_BS016 – Revision 3  
Effective Date: 01May2012

Reference: CS\_WI\_BS005

Copyright © 2012 Quintiles Transnational Corp. All rights reserved.  
The contents of this document are confidential and proprietary to Quintiles Transnational Corp. Unauthorized use, disclosure or reproduction is strictly prohibited.

---

## 7. STATISTICAL CONSIDERATIONS

### 7.1. ADJUSTMENTS FOR COVARIATES AND FACTORS TO BE INCLUDED IN EFFICACY ANALYSES

The following covariates and factors are to be used in the analyses. For details of their inclusion in the models, see the specific analysis section.

- Study period
  - PAC1
  - PAC2
  - PAC3
- Pooled region as finalised prior to the analysis during the BDR meeting
  - Pooled Region 01
  - Pooled Region 02
  - Pooled Region 03
  - Pooled Region 04
  - Pooled Region 05
  - Pooled Region 06
  - Pooled Region 07
  - Pooled Region 08
- Gender as captured on the Demographics eCRF (DEM)
  - Male
  - Female
- Asthma status as captured on the Asthma Diagnosis eCRF (ASTHMASCR)
  - No asthma
  - Controlled
  - Partly/Uncontrolled
- Baseline score
  - Represents the Baseline value of the relevant score being analysed from the BAE period

## 7.2. MULTI-CENTRE STUDIES

This study is to be conducted by multiple investigators at multiple centres internationally. Randomisation to treatment groups is not stratified by country/centre.

If a region has less than 5 subjects, pooling with other centre(s) is to be performed based on geographical region of the centres, providing the combination of data from small centres within a geographic region does not create a disproportionately large combined region. Distribution of subjects across pooled regions is to be assessed and pooling criteria finalised during the BDR meeting.

## 7.3. MISSING DATA

Missing safety data is not to be imputed. Partial start/stop dates for concomitant medications and AEs are not to be imputed. Treatment emergence of AEs and study period of medication use (prior or concomitant) is to be assigned based on available information as described in Appendix 2: Partial Date Conventions.

Daily derived efficacy scores (such as TRSS and CS) may be missing and will not be imputed as explained in Section 15.1.1 Primary Efficacy Variable & Derivation and Section 15.2.1 Secondary Efficacy Variables & Derivations.

Means of all derived daily efficacy scores during BAE, PAC1, PAC2 and PAC3 are to be calculated based on all days with non-missing scores within the respective periods defined in Section 3.1 General Description.

The primary efficacy analysis is to be performed using all available data on the assumption that the probability of missing observations is independent of unobserved measurements (missing at random). Therefore the missing values are not to be imputed for the primary analysis.

A Pattern-mixture model based on control-based imputation is to be utilised as the sensitivity analysis of the primary efficacy variable as described in Section 15.1.4 Sensitivity Analysis of Primary Efficacy Variable.

## 7.4. MULTIPLE COMPARISONS/MULTIPLICITY

For the primary efficacy analysis a hierarchical (step-down) approach is to be used to control the overall Type I error rate at 5%.

For declaring statistical significance, a step-down approach ( first 4 x 12 nmol versus placebo, then 4 x 20 nmol versus placebo and then 8 x 12 nmol versus placebo) is to be used to control the overall Type I error at 0.05.

Thus:

- Step 1: If 4 x 12 nmol HDM-SPIRE versus placebo is significantly different at the 0.05 significance level, move to Step 2. If there is no statistical significance, no further statistical significance is to be declared
- Step 2: If 4 x 20 nmol HDM-SPIRE versus placebo is significantly different at the 0.05 significance level, move to Step 3. If there is no statistical significance, no further statistical significance is to be declared

---

Document: TH005 SAP Version 2.docx  
Author: [name]

Version Number: 2.0  
Version Date: 24MAR2017

Template No: CS\_TP\_BS016 – Revision 3  
Effective Date: 01May2012

Reference: CS\_WI\_BS005

Copyright © 2012 Quintiles Transnational Corp. All rights reserved.  
The contents of this document are confidential and proprietary to Quintiles Transnational Corp. Unauthorized use, disclosure or reproduction is strictly prohibited.

---

- Step 3: If  $8 \times 12$  nmol HDM-SPIRE versus placebo is significantly different at the 0.05 significance level, declare statistical significance.

Statistical significance is declared for each step individually if  $p < 0.05$  and overall statistical significance is to be declared if Step 1, Step 2 and Step 3 has  $p < 0.05$ .

## 7.5. EXAMINATION OF SUBGROUPS

A treatment-by-pooled region interaction is to be added to the primary efficacy analysis as a supportive analysis as described in Section 15.1.5.2 Treatment-by-pooled region Interaction. In the event that the treatment-by-pooled region interaction term is observed to be statistically significant ( $p < 0.10$ ), the primary efficacy analysis as described in Section 15.1.3 Primary Analysis of Primary Efficacy Variable is to be analysed in subgroups of pooled region. Additionally, Baseline and Demographic Characteristics are to be summarised in subgroups of pooled region (see Section 10 Demographic and Baseline Characteristics).

## 8. OUTPUT PRESENTATIONS

The templates provided with this SAP describe the planned presentations for this study and therefore the format and content of the summary tables, figures and listings to be provided by Quintiles Biostatistics.

## 9. DISPOSITION AND WITHDRAWALS

Disposition and withdrawals are to be summarised for the ENR population.

Additionally, disposition and withdrawal summaries are to be presented for the following subgroups:

- Asthma status (Absent/Present/Missing) as captured on the Randomization eCRF (RAND)
  - Where Controlled and Partly/Uncontrolled are categorised as Present and
  - No Asthma is categorised as Absent
- TRSS categorised as TRSS  $< 16$ , TRSS  $\geq 16$  or Missing as captured on the Randomization eCRF (RAND)

The frequency (n) and percentage (%) of the following disposition and withdrawal categories are to be reported:

- Subjects screened
- Screen failures, defined as subjects where the Study Entry eCRF completed at the Screening visit indicates screening was not passed

---

Document: TH005 SAP Version 2.docx  
Author: [name]

Version Number: 2.0  
Version Date: 24MAR2017

Template No: CS\_TP\_BS016 – Revision 3  
Effective Date: 01May2012

Reference: CS\_WI\_BS005

Copyright © 2012 Quintiles Transnational Corp. All rights reserved.  
The contents of this document are confidential and proprietary to Quintiles Transnational Corp. Unauthorized use, disclosure or reproduction is strictly prohibited.

- Subjects that initially failed Screening may have been re-screened for eligibility following modifications to eligibility criteria in protocol amendments. Re-screened subjects are to be provided with a new Screening number and a link to the previous Screening number is to be captured on the Rescreening Status eCRF. Rescreened subjects that pass Screening are not to be counted as screen failures under their previous Screening numbers and are only to be accounted for once using the newly assigned Screening number and status.
- BAE failures, defined as subjects where the Study Entry eCRF (SENTRY) completed at the end of the BAE period indicates that the BAE period was not passed
- Randomised subjects, as indicated on the Randomisation eCRF (RAND). Subjects are to be eligible for randomisation if they passed both Screening as well as BAE.
- Completed study medication, early withdrawal from treatment period as well as primary reason for termination of study medication as entered on the End of Treatment eCRF (EOT)
  - Completed study medication is defined as receiving 8 doses of study medication from Visit 3A to Visit 3H
- Completed the study, early withdrawal from the study as well as primary reason for early withdrawal from the study as entered on the End of Study eCRF (EOS)

Completed the study is defined as completing the Follow-up Period (Visit 5) without prior early withdrawal from the study as indicated on the End of Study eCRF (EOS), regardless of completion of study medication as indicated on the End of Treatment eCRF (EOT). The frequency (n) and percentage (%) of subjects assigned to each analysis population is to be provided for the Randomized, ITT, PP and SAF populations, as well the reasons for exclusion from each population.

Percentages are to be calculated relative to the total number of subjects in the analysis population.

The following listings are planned for presentation:

- Subjects screening status (ENR population)
  - Includes eligibility criteria and inclusion/exclusion criteria exceptions
- Subject disposition (RND population)
- Analysis population assignment (ENR population)
- Major protocol deviations (RND population)

## 10. DEMOGRAPHIC AND BASELINE CHARACTERISTICS

Demographic data and Baseline characteristics are to be presented for the ITT population.

Additionally, demographic and baseline summaries are to be presented for the following subgroups:

- Asthma status (Absent/Present/Missing) as captured on the Randomization eCRF (RAND)

Document: TH005 SAP Version 2.docx  
Author: [name]

Version Number: 2.0  
Version Date: 24MAR2017

Template No: CS\_TP\_BS016 – Revision 3  
Effective Date: 01May2012

Reference: CS\_WI\_BS005

- Where Controlled and Partly/Uncontrolled are categorised as Present and
  - No Asthma is categorised as Absent
- TRSS categorised as TRSS <16, TRSS ≥ 16 or Missing as captured on the Randomization eCRF (RAND)
- Pooled region 01 to pooled region 08 as determined at the BDR meeting and documented in the BDR report

No statistical testing is to be performed for demographic or other Baseline characteristics.

Continuous demographic and Baseline characteristic variables (e.g. Age) are to be summarised using descriptive statistics. Categorical variables (e.g. Gender) are to be summarised by frequency (n) and percentage (%). Percentages are to be calculated relative to the total number of subjects in the analysis population with data available.

The following demographic and Baseline characteristics are to be reported for this study:

- Age (years) relative to date of informed consent is to be calculated using the following SAS code
  - Age = int((intck('month', <date of birth>, <date of informed consent> - (day(<date of informed consent>) < day(date of birth)))) / 12)
  - In the event that the date of birth is incomplete, the age at informed consent is to be imputed using the age as captured on the Randomisation eCRF
- Age group
  - 18 to 49
  - 50 to 70
- Gender from the System Screening eCRF (SCR)
  - Male
  - Female
- Race from the Demographics eCRF (DEM)
  - White
  - Black or African American
  - Asian
  - American Indian or Alaska Native
  - Native Hawaiian or other Pacific Islander
  - Not Collected
  - Other
- Ethnicity from the Demographics eCRF (DEM)
  - Hispanic or Latino
  - Not Hispanic or Latino
  - Not Reported

---

Document: TH005 SAP Version 2.docx

Author: [name]

Version Number:

2.0

Version Date:

24MAR2017

Template No: CS\_TP\_BS016 – Revision 3

Effective Date: 01May2012

Reference: CS\_WI\_BS005

Copyright © 2012 Quintiles Transnational Corp. All rights reserved.

The contents of this document are confidential and proprietary to Quintiles Transnational Corp. Unauthorized use, disclosure or reproduction is strictly prohibited.

- o Unknown
- Height (cm) from the Vital Signs eCRF (VS) at the Screening visit
- Weight (kg) from the Vital Signs eCRF (VS) at the Screening visit
- Body mass index (BMI) (kg/m^2)
- History of asthma from the Asthma Diagnosis eCRF (ASTHMASCR)
  - o Yes
  - o No
- Asthma status from the Asthma Diagnosis eCRF (ASTHMASCR)
  - o No Asthma
  - o Controlled
  - o Partly/Uncontrolled
- Asthma relationship to exposure to allergens from the Asthma Diagnosis eCRF (ASTHMASCR)
  - o No Relationship
  - o To HDM
  - o To Other Allergens

Demographic and Baseline characteristics are to be listed.

## 10.1. DERIVATIONS

Height is to be converted from inches (in) to cm as follows:

- Height (cm) = Height (in) x 2.54
- Weight is to be converted from lbs to kgs as follows:
- Weight (kg) = Weight (lb) x 0.453592

BMI is to be calculated as:

- BMI (kg/m^2) = Weight (kg) / [Height (cm) ÷ 100]

## 11. MEDICAL HISTORY

Medical History conditions are to be presented for the ITT population.

Document: TH005 SAP Version 2.docx  
Author: [name]

Version Number: 2.0  
Version Date: 24MAR2017

Template No: CS\_TP\_BS016 – Revision 3  
Effective Date: 01May2012

Reference: CS\_WI\_BS005

## 11.1. ALLERGY MEDICAL HISTORY

Allergy medical history includes all medical history conditions reported on the Allergy Medical History eCRF (AMHX).

The frequency (n) and percentage (%) of the following allergies are to be presented:

- House dust mite
- Cat
- Animal dander (other than cat)
- Cockroach
- Other additional allergies indigenous to a subject's area, under the following categories
  - Other dust mites
  - Mould
  - Grass
  - Weed
  - Tree
  - Animal dander
  - Other

Allergies specified as 'Other' category for 'Other additional allergies indigenous to the subject's geographic area' are only to be listed.

Percentages are to be calculated relative to the total number of subjects in the analysis population.

## 11.2. MEDICAL HISTORY OTHER THAN ASTHMA AND RHINOCONJUNCTIVITIS

Medical history other than asthma and Rhinoconjunctivitis includes all conditions captured on the Medical History – Other than Asthma and Rhinoconjunctivitis eCRF (MHX).

Medical history other than asthma and Rhinoconjunctivitis is to be coded using the Medical Dictionary for Regulatory Activities (MedDRA) Version 19.0

The frequency (n) and percentage (%) of conditions is to be presented by System Organ Class (SOC) and Preferred Term (PT). The summary is to be sorted by descending total frequency for each SOC, and within each SOC by the descending total frequency per PT.

Percentages are to be calculated relative to the total number of subjects in the analysis population.

---

## 11.3. SMOKING HISTORY

The frequency (n) and (%) of subjects within the following categories are to be presented for the ITT population as captured on the Smoking History eCRF (SMOK).

- Current smokers
- Former smokers
- Have never smoked

Percentages are to be calculated relative to the total number of subjects in the analysis population with data available.

Descriptive statistics are to be presented for the following categories captured on the Smoking History eCRF (SMOK) for current smokers and former smokers:

- Average number of cigarettes per day
- Average number of cigars per day
- Average number of pipes per day
- Number of years smoked
- Number of pack years

---

## 12. MEDICATIONS

Medications are to be presented for the ITT population and coded using the World Health Organization-Drug Dictionary (WHO-DD) Version 01MAR2016.

Prior (P) and concomitant (C) medications are to be presented by generic name for Allergy Medications and Other Medications respectively.

- Allergy medications are defined as medications where the Concomitant Medications eCRF (CMDT) question, 'Is the medication used for HDM allergy?' or 'Is the medication used for other allergy?' are indicated as 'Yes'
- Other medications are defined as medications where the Concomitant Medications eCRF (CMDT) question, 'Is the medication used for HDM allergy?' and 'Is the medication used for other allergy?' are indicated as 'No'

The summaries are to be sorted by descending total frequency per generic name.

Prior and concomitant medications are defined as follows:

- 'Prior' medications are medications which started and ended prior to the first administration of study medication.

---

Document: TH005 SAP Version 2.docx  
Author: [name]

Version Number: 2.0  
Version Date: 24MAR2017

Template No: CS\_TP\_BS016 – Revision 3  
Effective Date: 01May2012

Reference: CS\_WI\_BS005

---

- 'Concomitant' medications are medications which:
  - Started on or after the first administration of study medication and continues during the study and/or up to the end of study, OR
  - started prior to first administration of study medication and ended on or after the date of first administration of study medication or were ongoing AND
  - are not part of the medications from the rescue medication plan as specified in protocol Appendix 3: Rescue Medication Package Description and Rescue Medication Plan

See Appendix 2 for handling of partial dates for medications.

Separate by-subject listings for allergy medications and other medications are to be presented.

## **13. STUDY MEDICATION EXPOSURE**

Exposure to study medication in days is to be presented for the ITT population.

Exposure to study medication is to be summarised by descriptive statistics and treatment group.

The date of first study medication administration is to be taken from the Study Medication Administration eCRF (SDA1). The date of last study medication administration is to be taken as the last available administration date on the Study Medication Administration eCRF (SDA1/2).

Additionally exposure to study medication is to be summarised as the frequency (n) and percentage (%) of subjects receiving study medication at each Study Medication Administration (Visits 3A-3H) visit. Subjects are considered to have received study medication at each visit if the response to the question 'Was the study medication administered in accordance with the protocol?' is indicated as 'Yes' on the Study Medication Administration eCRF (SDA1/2).

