### **13.1. DERIVATIONS**

Duration of exposure (days) = (Date of last study medication administration – Date of first study medication administration) + 1.

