## 14.1. DERIVATIONS

Compliance with double-blind study medication is to be calculated as the number of injections received (as indicated on the Study medication Administration eCRF (SDA1/2)) divided by the planned number of injections, expressed as a percentage, see calculations below:

- Compliance over first 4 doses = (Number of doses received from Visit 3A to Visit 3D / Planned number of doses [4]) X 100
- Compliance over last 4 doses = (Number of doses received from Visit 3E to Visit 3H / Planned number of doses [4]) X 100
- Overall compliance = (Total number of doses received / Planned number of doses [8]) X 100

Subjects are expected to receive one dose per visit from Visit 3A to Visit 3H for a total of 8 doses.

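### SAP 13 counts an injection as received only if it was given according to the protocol, so the by-visit exposure table omits injections given with a deviation

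*SAP*

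**What the plan says.** SAP 13 gives two summaries of exposure.

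- **By visit.** The table reports the number and percentage of "subjects receiving study medication at each Study Medication Administration (Visits 3A-3H) visit". Receipt is then defined: "Subjects are considered to have received study medication at each visit if the response to the question" that follows is answered 'Yes'. The item and its source are "Was the study medication administered in accordance with the protocol?' is indicated as 'Yes' on the Study Medication Administration eCRF" (SDA1/2). No other rule for receipt is given for this table.
- **Duration.** This uses dates alone: "The date of last study medication administration is to be taken as the last available administration date on the Study Medication Administration eCRF" (SDA1/2). SAP 13.1 then sets "Duration of exposure (days) = (Date of last study medication administration – Date of first study medication administration) + 1". Neither statement asks whether the injection complied with the protocol.

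Three other parts of the SAP also depend on doses received. SAP 14.1 bases compliance on the "number of injections received (as indicated on the Study medication Administration eCRF (SDA1/2)) divided by the planned number of injections" and does not name the field. SAP 5.3 and 5.4 require at least one dose for the ITT and Safety populations, without an adherence condition. SAP 9 defines completion of study medication as receipt of all eight doses.

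**The concern.** The table is labelled as receipt, but the item behind it asks about adherence. A 'No' can mean two different things: no injection was given, or an injection was given and something about it broke the protocol. The rule puts both under not received. The second group was exposed to study medication, and an exposure table exists to show who was exposed and when.

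At stake is whether the table is accurate and agrees with the other exposure figures in the same report. A reader who sees a subject missing from one dosing visit will take it that the dose was skipped, when it may have been injected with a deviation.

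**Working it through.** The plan states no figure on this point, so there is nothing to reproduce. The check sets the rules side by side and follows single subjects through them.

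**Step 1. How each rule treats one visit.**

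| What happened at the visit | By-visit table (SAP 13) | Duration (SAP 13, 13.1) | At least one dose (SAP 5.3, 5.4) |
|---|---|---|---|
| Injected, protocol followed | received | date counts | counts |
| Injected, protocol breached | not received | date counts | counts |
| Not injected | not received | no date | does not count |

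The rules differ only in the middle row. (The Safety population also needs a post-baseline safety assessment.)

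**Step 2. Which injections fall in the middle row.**

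- An injection given later after reconstitution than protocol 5.4 permits; one limit there is one hour where no ISO Class 5 environment is available.
- An injection at a volume that protocol 5.5.1 does not allow.
- An injection at an interval that protocol 5.5.2 does not allow.

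Two look-alikes do not belong there. A 50 μL dose after a trigger reaction is what 5.5.1 directs. A visit moved by up to 7 days is what 5.5.2 allows. Both comply, so both should be 'Yes'.

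**Step 3. One subject, eight injections, k of them with a deviation.** Share of visits shown as received = (8 − k)/8.

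- k = 1: 7/8 = 87.5%
- k = 2: 6/8 = 75%
- Injections actually received in both cases: 8/8 = 100%

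**Step 4. Conflict within SAP 13.** Suppose doses fall exactly on schedule and the deviating one is the last (Visit 3H, Week 28).

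- Duration from dates: 28 × 7 + 1 = 197 days.
- The by-visit table shows Visit 3G (Week 24) as the last dose received, which would correspond to 24 × 7 + 1 = 169 days.

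In the extreme case, a subject whose only injection deviated has a duration of 1 day and belongs to the ITT population, yet appears at 0 of 8 visits.

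**Step 5. Scale at one visit.** With about 165 subjects per group, all injected, each deviating injection lowers the displayed percentage by 100/165 = 0.6 points. The documents give no deviation rate. Purely as an assumed range, 1% to 10% of injections at a visit would be 1.65 to 16.5 subjects (about 2 to 17), and the table would show 99% to 90% where the true figure is 100%.

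**The case against.** The strongest reply is that the form cannot be seen. Sites may have used the item simply to record given or not given, may have been told to ignore minor deviations, or may have had follow-up fields after a 'No'. The SAP also writes 'if' and not 'only if'. Both points are fair. The first means that nobody can say from the documents how often the rule would misclassify. The second carries little weight, because this sentence is the only definition of receipt for the table.

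It can also be said that the table is descriptive and little hangs on it. That stands, and it rules out two stronger readings.

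- **Safety rates.** A reader might infer that this table is the denominator for per-dose reactions, so that safety rates would be distorted. The documents do not support that. The exposure table is on the ITT population, whereas SAP 16 puts all safety outputs on the Safety population. SAP 16.1.8 ties events within 24 hours of a dose to dosing date and time. SAP 16.7.2 summarises local reactions by grade and visit without reference to this item. Nor does anything link deviations to doses at which reactions are more likely.
- **Compliance.** A reader might infer that the compliance table must contradict the exposure table. SAP 14.1 names no field. If it uses the same item, the two tables agree and both undercount; if it uses dates, they can differ. The wording leaves this open.

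Major protocol deviations are listed under SAP 9, so some of these injections may be visible there. A deviation listing does not correct the exposure count.

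**Conclusion.** The point holds and is minor. As written, SAP 13 shows an injection given in breach of the protocol as not received, and so disagrees with the date-based duration in the same section and with the dose condition in the ITT and Safety definitions. The error has one direction: each such injection removes one subject from one visit's count.

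The conclusion rests on reading the SAP sentence as the complete definition of receipt, and on sites answering the item as it is worded. The effect is confined to one descriptive table, plus compliance if that draws on the same item. No efficacy analysis, analysis population or planned safety rate is shown to change.

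A reader might want a total, for example 660 × 8 = 5,280 planned injections, of which an assumed 1% to 3% would be 53 to 158. The documents support neither part: they give no deviation rate, and 5,280 requires every subject to receive all eight doses. The number affected in this trial cannot be estimated from them.

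**What to change.** In SAP 13, replace the rule for receipt along these lines:

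> A subject has received study medication at a visit if an administration date is recorded for that visit on SDA1/2, whatever the answer to the adherence item.

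Add a row or small table, by visit and treatment group, counting injections given with a 'No' to the adherence item. In SAP 14.1, state that injections received are counted by the same definition.

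The cost is two or three sentences and one extra count. No new data are needed, because SAP 13 already takes administration dates from this form. Before adopting the wording, check the eCRF completion instructions to confirm that a date is entered only when an injection was given.
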